#### **7.2.5** Blood Components for Transfusion

For all elective red cell transfusions, leukocyte-reduced units matched for the phenotype of the patients (as described above) will be used. Where exact matching for all the specified blood groups proves impractical (*e.g.*, for any of the blood groups M, N, and S compromising the MNS system [MNS]), local sites will decide on the best matched donor units to be used. Cytomegalovirus (CMV) matching (*i.e.*, CMV seronegative units for CMV-seronegative patients) will not be required for this study because it will limit the inventory for antigen matching.

If the cross-match is incompatible, the RBC units that are Coomb's crossmatch-incompatible will be selected (e.g., phenotype-matched or least incompatible) for issue at the discretion of the local site's Transfusion Service Medical Director or equivalent person, where available. Such instances will be documented, along with consent signatures obtained from ordering physicians, according to best practices in blood bank policies and procedures.

For emergency transfusions, the transfusion laboratory may consider using emergency Group O Rhesus negative units if phenotyped units are not available.

Blood plasma therapy will be blood-type specific. Platelets will be blood type compatible whenever possible, and if not, will have been tested and found not to have high titer anti-A or anti-B.

### **7.2.6** Management of Pneumonitis

Pneumonitis has been infrequently observed in patients receiving magnolimab. It is currently unknown if Hu5F9-G4 (magnolimab) increases the risk of pneumonitis.

In instances of suspected pneumonitis, first rule out non-inflammatory causes (e.g., infections, etc.). If a non-inflammatory cause is identified, treat accordingly and continue therapy per protocol. Evaluate with imaging, e.g. chest x-ray or computed tomography, and pulmonary consultation.

Management of potential pneumonitis is detailed below and follows American Society of Clinical Oncology (ASCO) guidelines for immune-related adverse events (Brahmer et al., 2018). Patients who experience Grade 3-4 pneumonitis will be permanently discontinued from study treatment.

Pneumonitis		
CTCAE Grade of Pneumonitis	Management	Follow-Up
Grade 1 Radiographic changes (CXR or CT) only.	Monitor for signs and symptoms weekly and consider monitoring with CXR.  Consider pulmonary and infectious disease consults.	Consider re-imaging with CT in 3-4 weeks as clinically indicated.  May resume magrolimab with radiographic evidence of improvement or resolution.  If no clinical improvement or worsening, treat as Grade 2.
Grade 2 Mild to moderate new symptoms.	Interrupt magrolimab therapy per protocol. Pulmonary and infectious disease consults. Consider empirical antibiotics. Monitor signs and symptoms every 2-3 days; consider hospitalization. 1 mg/kg/day oral prednisone or IV equivalent. Consider bronchoscopy, lung biopsy.	Re-image every 1-3 days.  If improving to baseline, taper corticosteroids over 4-6 weeks and resume magrolimab therapy per protocol.  If no clinical improvement after 48-72 hours or worsening, treat as Grade 3-4.
Grade Severe new symptoms; new/ worsening hypoxia; life- threatening.	Discontinue magrolimab therapy. Hospitalize. Pulmonary and infectious disease consults. 1-2 mg/kg/day methylprednisolone IV or IV equivalent. Add empirical antibiotics and consider prophylactic antibiotics for opportunistic infections. Consider bronchoscopy, lung biopsy.	If improving to baseline, taper corticosteroids over 4-6 weeks.  If no clinical improvement after 48 hours or worsening, consider additional immunosuppression (e.g., infliximab, cyclophosphamide, IV immunoglobulin, mycophenolate mofetil).

CT = computed tomography; CTCAE = Common Terminology Criteria for Adverse Events; CXR = chest x-ray; IV = intravenous.

# **7.2.7** Management of Thromboembolic Events

Thromboembolic events including deep vein thromboses and pulmonary embolisms have been reported in some patients receiving Hu5F9-G4 (magrolimab), sometimes early in therapy.

- No clear or consistent relationship between clinical and thromboembolic events and Hu5F9-G4 (magrolimab) use has been observed.
- Close monitoring for symptoms of thromboembolic events is required.
- Patients should be treated as per standard of care.

# 7.3 Dinutuximab (Unituxin®) AE Management and Dose Modification Guidelines

For detailed information regarding management of AEs associated with dinutuximab (Unituxin®), please refer to the most

current version of the dinutuximab (Unituxin®) prescribing information.

The most common adverse drug reactions (≥ 25%) with dinutuximab are pain, pyrexia, thrombocytopenia, lymphopenia, infusion reactions, hypotension, hyponatremia, increased alanine aminotransferase, anemia, vomiting, diarrhea, hypokalemia, capillary leak syndrome, neutropenia, urticaria, hypoalbuminemia, increased aspartate aminotransferase, and hypocalcemia.

#### **7.3.1** Discontinuation of Dinutuximab

The administration of dinutuximab will be discontinued for the following adverse events that are possibly, probably or definitely related to dinutuximab administration:

Table 8: Adverse Reactions Requiring Permanent Discontinuation of Dinutuximab

Severity	Adverse Reaction
Grade 3 or 4	Anaphylaxis
Grade 3 or 4	Serum sickness
≥Grade 3	Pain unresponsive to maximum supportive measures
Grade 4	Sensory neuropathy
Grade 3	Sensory neuropathy that interferes with daily activities for more than 2 weeks
≥Grade 3	Peripheral motor neuropathy
≥Grade 3	Decrease in vision if not improved to Grade 1 or better before next dose is due.
Grade 4	Hyponatremia despite appropriate fluid management

#### **7.3.2** Dose Modification of Dinutuximab

The administration of dinutuximab will be modified for the following adverse events that are possibly, probably or definitely related to dinutuximab administration.

# 7.3.2.1 Treatment of dinutuximab-induced hypotension (without evidence of allergic reaction)

- a. If hypotension is severe and accompanied by poor perfusion, end organ dysfunction, or acidemia Pediatric Advanced Life Support (PALS) guidelines should be followed and dinutuximab infusion discontinued.
- b. In the absence of poor perfusion, end organ dysfunction or acidemia, moderate hypotension is defined as:
  - i. Symptomatic decreases in blood pressure (BP) and/or
  - ii. Systolic BP < 5th percentile based on age and height and baseline BPs OR
  - iii. Systolic or diastolic BP decrease by > 20% below baseline.
- c. For patients with moderate hypotension in the absence of poor perfusion, end organ dysfunction, or acidemia:
  - i. Immediately hold dinutuximab
  - ii. Give normal saline bolus (20 mL/kg as rapidly as possible)
  - iii. Stop or adjust doses of narcotics and sedating H1 blockers
  - iv. Consider use of Trendelenberg position
- d. If hypotension persists after the above measures have been taken:

- i. Reassess perfusion and end organ function
- ii. Follow PALS algorithm if indicated
- iii. Repeat NS bolus OR
- iv. Consider use of albumin if albumin < 3 gm/dL
- v. Consider use of RBCs if Hb < 10 gm/dL
- vi. Consider use of platelets if count < 50,000/uL
- vii. Consider transfer to intensive care unit.
- e. If hypotension persists after 2 volume boluses, give an additional bolus and prepare to administer pressors
  - i. Epinephrine or norepinephrine is preferred over dopamine if possible

## f. Resumption of dinutuximab

- i. For patients whose hypotension resolves promptly and completely with limited volume resuscitation (≤ 40 mL/kg) and without requirement for pressor support, dinutuximab may be restarted at 50% of the previous infusion rate. The dinutuximab may be restarted on same day if it is possible to do so within 20 hours of the start of the day's infusion. If blood pressures are stable for 2 hours, the infusion may be given at full rate for that day and subsequent days. If the patient again experiences hypotension requiring multiple volume boluses (e.g., > 40 mL/kg) when dinutuximab is given at full rate but tolerates the 50% infusion rate, the remaining days' doses of dinutuximab should be given at the 50% rate of infusion. If > 20 hours have elapsed since the start of the infusion, restart dinutuximab the following day.
  - 1. If blood pressures are stable for 2 hours after resumption of dinutuximab at the reduced rate, the remainder of the antibody infusion may be given at the full rate
  - 2. If hypotension recurs at the reduced rate, the measures above should again be taken and no further dinutuximab should be given that day. The antibody infusion may be restarted the following day after ensuring that the patient is volume replete. The antibody rate upon resumption of treatment should be 50% of the initial rate. If blood pressures are stable for 2 hours, the infusion may be given at full rate for that day and subsequent days. If the patient's blood pressures are only stable at the 50% rate and not at full rate, the remaining days' doses of dinutuximab should be given at the 50% rate of infusion.
- ii. For patients who require multiple volume boluses for hemodynamic stabilization, dinutuximab should be resumed the following day at 50% of the initial infusion rate.
  - 1. If blood pressures are stable for 2 hours after resumption of dinutuximab at the reduced rate, the remainder of the antibody infusion may be given.
  - 2. If hypotension recurs at the reduced rate, the measures above should again be taken and no further dinutuximab should be given that day. The antibody infusion may be restarted the following day after ensuring that the patient is volume replete. The antibody rate upon resumption of treatment should be 50% of the initial rate. If blood pressures are stable for 2 hours, the infusion may be given at full rate for that day and subsequent days. If the patient's blood pressures are only stable at the 50% rate and not at full rate, the remaining days' doses of dinutuximab should be given at the 50% rate of infusion.
- iii. For patients who require pressors for treatment of hypotension, if blood pressure is stable off pressors for at least 6 hours, administration of dinutuximab may be resumed at 50% of the initial infusion rate on the day following the hypotensive episode. Care should be taken to ensure that the patient is volume replete. Dinutuximab should not be given to patients who continue to require pressor support. Patients who require pressor support for ≥ 24 hours due to treatment-related hypotension despite appropriate volume resuscitation should discontinue protocol therapy. Patients

who again require pressor support when dinutuximab is resumed should discontinue protocol therapy.

# 7.3.2.2 Treatment of Allergic Reactions/Infusion Reactions

- a. Mild allergic reactions/infusion reactions to dinutuximab infusion
  - i. A mild allergic reaction is limited to rash, flushing, urticaria, mild dyspnea Grade 1 or 2
  - ii. The following recommendations do NOT apply to Grade 3 or 4 allergic reactions, including anaphylaxis
  - iii. Management
    - Decrease rate of dinutuximab to 50% of full rate
    - Perform serial exams at bedside
    - Administer H1 blocker (diphenhydramine, cetirizine recommended)
    - Administer H2 blocker
    - When symptoms resolve, resume original infusion rate
    - If symptoms recur when original rate is resumed, decrease to 50% rate again
    - Infusion must be stopped after 20 hours (whether the full dose of dinutuximab has been administered or not); document total amount of drug given in the 20-hour time period
- b. Moderate to severe allergic reactions/infusion reactions to dinutuximab infusion
  - i. Moderate to severe reactions include any of the following: symptomatic bronchospasm, allergy-related edema/angioedema, hypotension, or anaphylaxis Grade 3 or 4
  - ii. The following recommendations do NOT apply to Grade 1 or 2 allergic reactions
  - iii. Management: Immediately hold dinutuximab
    - Assess airway, breathing and circulation
    - Follow institutional guidelines for rapid response team notification if clinically indicated
    - For airway concerns
      - o Administer oxygen and albuterol immediately for bronchospasm
      - Administer IV diphenhydramine
      - Administer epinephrine (1:1000 IM recommended) immediately if upper airway involved or if airway issues are accompanied by cardiovascular collapse
      - O Administer IV hydrocortisone (1-2 mg/kg) if the patient has frank anaphylaxis with cardiorespiratory collapse OR if  $\geq$  2 doses of epinephrine are required OR if moderate to severe symptoms recur upon rechallenge with dinutuximab
    - For hypotension in the setting of allergic reaction
      - o Give normal saline bolus (20 mL/kg as rapidly as possible)
      - O Stop or adjust doses of narcotics and sedating H1 blockers
      - Consider use of Trendelenberg position
      - o See previous section for management of persistent hypotension
    - For patients with mild bronchospasm or angioedema that does not impact breathing, completely resolves without the use of epinephrine and hydrocortisone and for patients whose hypotension resolves following volume bolus, dinutuximab may be resumed at 50% of the previous rate of infusion on the same day as the reaction occurred. If symptomatic angioedema or asymptomatic bronchospasm recurs when the dinutuximab is restarted, discontinue immunotherapy for that day and if symptoms/signs resolve completely that day, resume the next day with additional

pre-medication of hydrocortisone 1-2 mg/kg IV. For this re-challenge, the infusion should be given in an ICU setting.

- For patients whose bronchospasm or angioedema requires the use of systemic epinephrine, protocol therapy should be discontinued.
- For patients with bronchospasm or angioedema that does not require systemic epinephrine but whose hypotension requires more extensive volume resuscitation, guidance in Section 7.3.2.1 should be followed.

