### 6.5 Criteria for Removal from Protocol Therapy and Off Study Criteria

# **6.5.1** Criteria for Removal from Protocol Therapy

In the absence of treatment delays due to adverse event(s), treatment may continue for to a maximum of 12 cycles (9 months of combination therapy) [except in cohort B4, resectable, pulmonary only relapsed osteosarcoma, who may continue combination therapy for a total of 5 cycles after pulmonary resection] or until one of the following criteria applies:

Disease progression

- Intercurrent illness that prevents further administration of treatment.
- Unacceptable adverse event(s), including, but not limited to, any one of the following:
  - o Patients who have Grade 4 infusions reactions occurring with the first dose of Hu5F9-G4 (magrolimab) or dinutuximab will be permanently discontinued from treatment.
  - Patients who receive Hu5F9-G4 (magrolimab) premedication with corticosteroids and still have a Grade 3 or 4 infusion reaction on subsequent doses will generally be permanently discontinued from treatment, unless continued therapy is approved by the Study PI, Site PI and Sponsor.
  - O Patients who receive dinutuximab and experience any of the AEs listed in Table 8: Adverse Reactions Requiring Permanent Discontinuation of Dinutuximab

or recur after appropriate management as outlined in Section 7.3.2.

- Patient who develops a DLT during the "single agent Safety Lead-In" will be removed from additional therapy on this study.
- General or specific changes in the patient's condition render the patient unacceptable for further treatment in the judgment of the investigator.
- Clinical progression of disease
- Patient non-compliance
- Pregnancy
  - All women of childbearing potential should be instructed to contact the investigator immediately if they suspect they might be pregnant (e.g., missed or late menstrual period) at any time during study participation.
  - The investigator must immediately notify CTEP in the event of a confirmed pregnancy in a patient participating in the study.
- Termination of the study by sponsor
- The drug manufacturer(s) can no longer provide the study agents.

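### Grade 3 or 4 anaphylaxis and Grade 4 first-dose infusion reactions to dinutuximab require a permanent stop under Table 8 and 6.5.1, but 7.3.2.2.b covers them without exclusion and permits same-day resumption

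*Combined protocol and SAP*

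**What the plan says.** **Permanent stop.** Section 7.3.1 introduces "Table 8: Adverse Reactions Requiring Permanent Discontinuation of Dinutuximab". Its first row is "Grade 3 or 4 Anaphylaxis", with no condition about recovery. Section 6.5.1 turns the table into a removal criterion by listing, among unacceptable adverse events, "Patients who receive dinutuximab and experience any of the AEs listed in Table 8". The same section adds: "Patients who have Grade 4 infusions reactions occurring with the first dose of Hu5F9-G4 (magrolimab) or dinutuximab will be permanently discontinued from treatment".

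**Hold and resume.** Section 7.3.2.2.b sets its scope as follows: "Moderate to severe reactions include any of the following: symptomatic bronchospasm, allergy-related edema/angioedema, hypotension, or anaphylaxis Grade 3 or 4". It excludes Grade 1 and 2 allergic reactions. The instruction at onset is to hold dinutuximab. Same-day restart at half rate is then permitted for two groups. One is patients with mild bronchospasm or angioedema that leaves breathing unaffected and clears without epinephrine and hydrocortisone. The other is described in these words: "for patients whose hypotension resolves following volume bolus, dinutuximab may be resumed at 50% of the previous rate of infusion on the same day". Protocol therapy ends only where bronchospasm or angioedema needs systemic epinephrine.

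**Cross-reference.** For allergic hypotension that persists, 7.3.2.2.b points to the preceding section, 7.3.2.1. Its last bullet also sends there patients with bronchospasm or angioedema who did not need systemic epinephrine but needed more fluid. Under 7.3.2.1.f.iii, once blood pressure has held for six hours or more without pressors, "administration of dinutuximab may be resumed at 50% of the initial infusion rate on the day following the hypotensive episode".

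**The concern.** A site that reads Table 8 and 6.5.1 gives the patient no further dinutuximab. A site that reads 7.3.2.2.b may restart the infusion the same day. Both follow the protocol as written, and the event is a severe or life-threatening reaction in a child or young adult. Nothing in 6.5.1, 7.3.1 or 7.3.2 says which text prevails.

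The omission shows by contrast with the other agent. The magrolimab infusion-reaction table in 7.2.1 repeats that agent's Grade 4 first-dose stop; the dinutuximab management section does not repeat its own.

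There is a smaller statistical consequence. Where a reaction is exempt from the DLT definition, the section a site follows can decide whether an Arm A patient is counted or replaced.

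**Working it through.** No sample size or error rate is involved, so the check is a comparison of the rules, reaction by reaction.

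| Reaction to dinutuximab | Table 8 / 6.5.1 | 7.3.2.2.b | Result |
|---|---|---|---|
| Grade 3 or 4 anaphylaxis; hypotension clears after a bolus; no systemic epinephrine for the airway | Permanent stop | Hold; same-day restart permitted | Conflict |
| Grade 4 infusion reaction, first dose; hypotension clears after a bolus; no systemic epinephrine for the airway | Permanent stop | Hold; same-day restart permitted | Conflict |
| Bronchospasm or angioedema needing systemic epinephrine | Stop if anaphylaxis or Grade 4 first dose | Stop | No conflict |
| Grade 3, not anaphylaxis | No stop on grade alone | Restart may be permitted | No conflict |
| Grade 4 after the first dose, not anaphylaxis | No specific stop | Restart may be permitted | No direct conflict |

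Rows four and five rest on the scope of 6.5.1. Its only infusion-reaction rule reaching Grade 3 begins "Patients who receive Hu5F9-G4 (magrolimab) premedication with corticosteroids and still have a Grade 3 or 4 infusion reaction on subsequent doses", so it concerns magrolimab. The infusion-reaction rule that names dinutuximab is limited to Grade 4 and the first dose.

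**Cross-reference to 7.3.2.1.** The title of 7.3.2.1 restricts it to hypotension with no sign of allergy, yet 7.3.2.2.b sends allergic hypotension there in two places. If a site follows that pointer through to f.iii, a Grade 4 first-dose reaction treated with pressors for under 24 hours could be restarted the next day, while 6.5.1 removes the patient. This is a secondary inconsistency because it depends on how far the pointer is meant to reach.

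**Size.** Inputs: maximum enrollment of 82 (Section 9.3.3: 12 + 3 × 20 + 10 = 82), and anaphylaxis in the under-3% column of the dinutuximab CAEPR (Section 10.1.1.2).

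82 × 0.03 = 2.46, so about 2 patients at most in expectation. No frequency is given for Grade 4 first-dose infusion reactions, so that part cannot be sized.

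**Dose-finding.** Section 6.3 counts Grade 3 or higher, at least possibly related non-hematological events in Cycle 1 as DLTs unless exempted. A counted DLT stays a DLT whether or not dinutuximab restarts. Two exemptions bear on these reactions: item h (Grade 3 infusion reactions without optimal pretreatment) and item n (Grade 3–4 hypotension that settles within 8 hours). Section 9.2.1 replaces Arm A patients who discontinue before the safety evaluation for a non-DLT adverse event. For an exempt event, a permanent stop can therefore lead to replacement, while a restart keeps the patient evaluable.

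**The case against.** A consistent reading is available. Section 7.3.1 lists events that end dinutuximab, and 7.3.2 deals with events for which it is modified. The restart bullet is permissive and describes milder groups without naming anaphylaxis. On this view 7.3.2.2.b gives acute care for the whole spectrum, and 6.5.1 need not be repeated in every management section. The sentence in 6.5.1 after the Table 8 reference is broken in the available text. It may separate Table 8 events, which lead to removal, from 7.3.2 events, which lead to removal on recurrence.

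That reading is possible but nowhere stated. Even if accepted, anaphylaxis of Grade 3 or 4 appears both in Table 8 and in the scope of 7.3.2.2.b. Nor can a site infer from pattern that Table 8 wins. Section 7.3.2.9 repeats Table 8's serum sickness stop, but 7.3.2.10 allows a reduced dose next cycle after resolved Grade 3 motor neuropathy, which Table 8 lists for permanent discontinuation.

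The epinephrine rule removes part of the conflict, as the third row of the table shows. It does not cover reactions in which hypotension is the leading feature.

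Three further limits stand:

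- A reader might infer that all Grade 3–4 dinutuximab allergic or infusion reactions are affected. The documents do not support this, because rows four and five have no opposing stop rule.
- A reader might size the problem from the any-grade frequencies of allergic reaction (up to 20%, Section 10.1.1.2) or infusion reaction (at least 25%, Section 7.3). Neither measures the two events in conflict, and 10.1.1.2 itself appears to place infusion related reaction under 3%.
- A reader might infer that dose-finding as a whole mixes two re-exposure policies. The effect is confined to DLT-exempt events, and every patient who receives any study drug remains evaluable for toxicity under 9.2.1.

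**Conclusion.** The contradiction is real for two events: Grade 3 or 4 anaphylaxis, and a Grade 4 infusion reaction with the first dinutuximab dose. For each, one rule removes the patient permanently and another, followed as written, permits re-exposure the same day. The reference to 7.3.2.1, with its possible next-day restart after pressors, is a secondary inconsistency.

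The expected number is small: about 2 of 82 for anaphylaxis, and unknown for Grade 4 first-dose reactions. The anaphylaxis figure assumes full enrollment and that the any-grade CAEPR frequency for dinutuximab carries over to the combination; it is an expectation, not a limit on what could be observed. The importance lies in the consequence for the affected patient rather than in frequency. This review takes no position on which rule is clinically right.

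**What to change.** The clinical team should reconcile 6.5.1, Table 8 and 7.3.2.2.b, together with the references from 7.3.2.2.b to 7.3.2.1, so that each of the two events has one stated outcome. A sentence at the head of 7.3.2 should say which section governs when an event falls under more than one. The restart bullets in 7.3.2.2.b, and in 7.3.2.1.f where they are reached by cross-reference, should point back to 6.5.1 and Table 8. The title of 7.3.2.1 should agree with the use that 7.3.2.2.b makes of it. The content of the rule is for the clinical team to decide.

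The cost is protocol wording in the next amendment, with no additional patients, tests or visits.
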